2.7.2.3.3 Other Exploratory Measures

Demographic questionnaire. In the proposed RCT, we will design a parent-report questionnaire to collect demographic information such as child age and gender, family structure, family income, employment of a domestic helper, as well as parents' age, occupation, and education. Parents will also be asked to report the type(s) of clinical diagnosis or disability which their child has and rate the severity of their child's DD as a whole using a 4-point Likert scale (1 = *very mild* and 4 = *severe*). The demographic and

clinical information will be used to characterize children and their parents in the intervention and control groups for comparison.

Additionally, we consider that the availability and intensity of early intervention services may have an effect on children's functional performance and participation based on literature. Therefore, this questionnaire will also ask parents to report the type(s) and duration of early intervention service(s) their child has received in the past month. The information in the total number of the early intervention service hours will be categorized and used as a control variable adjusted for baseline differences in the analysis of the efficacy of OPC.

Pediatric Evaluation of Disability Inventory Computer-Adaptive Tests (PEDI-CAT).

The PEDI-CAT is a parent-report, computer-based assessment of children's functional performance across four domains: daily activity, social/cognitive function, mobility, and responsibility. In the proposed RCT, we will select the use of the first two domains, operated by the speedy feature, for the purpose of exploring the improvement in children's daily activities and social/cognitive function. The speedy feature allows reducing administration time by selecting suitable 10–15 items to assess based on the relative difficulty of preceding items and parents' responses to those items (instead of completing a full set of items). In each PEDI-CAT item, parents rate their child's typical performance using a 4-point Likert scale (1 = *unable* and 4 = *easy*). Scaled scores of each domain are derived based on the estimates of the placement of individual children along the hierarchical scales that have been calibrated using item-response theory in the standardization samples. The PEDI-CAT scaled scores are on a 20–80 metric and have been recommended for use to evaluate changes over time. The PEDI-CAT has demonstrated excellent agreement with the full-length version (Pearson's $r = 0.94\text{--}0.99$) and satisfactory test-retest reliability (ICC = 0.86–0.92).

Environmental support scale of the YC-PEM. In the community section of the YC-PEM mentioned earlier, parents will also be asked to evaluate the impact of the types of environmental features (10 items) and resources (seven items) regarding their child's participation in community settings. This scale is selected for use because we would like to explore whether parents who receive OPC have higher perceived environmental support for their children's community participation. In the environmental support scale, a 3-point Likert scale is used to assess the level of parents' perceived impact of environmental features (1 = *usually makes it harder* and 3 = *no impact/usually helps*) and resources (1 = *usually no* and 3 = *not needed/usually yes*) on participation, respectively. Total scores are generated by averaging all items on this scale, with high scores indicating greater environmental support. This environmental support scale has acceptable internal consistency ($\alpha = 0.83$) and test-retest reliability (ICC = 0.78).

Session Rating Scale (SRS). The SRS is a four-item visual analog scale that assesses therapeutic alliance at the end of each session, and this scale is used because it provides insight into the potential mechanism of parents' intrinsic motivation to enact actions during

OPC. Each of the four items captures a key dimension of effective therapeutic relationships, including respect and understanding, relevance of the goals and topics, approach used in therapy, and overall alliance. Parents are asked to place a mark on a 10-cm line nearest the pole that best describes their experience with their OPC coach. Total scores are generated by summing up the marks made by parents measured to the nearest centimeter on each of the four lines. Higher scores indicate greater therapeutic alliance. The SRS has been reported to be internally consistent ($\alpha = 0.88\text{--}0.96$) and reliable over time ($r = 0.63$).

Health Care Climate Questionnaire (HCCQ). The HCCQ assesses people's perceptions of health care practitioners' autonomy support in a given program grounded by self-determination theory. It consists of 15 items rated on a 7-point Likert scale (1 = *strongly disagree* and 7 = *strongly agree*). One example item is "I feel that my health-care practitioner has provided me with choices and options about regular exercise." Total scores are calculated by averaging all item scores, with higher scores indicating greater autonomy support. The HCCQ has been adapted by Chan et al. for use in the physiotherapy context by replacing "health-care practitioner" with "physiotherapist" and eliminating the statement of the specific program (e.g., regular exercise). In the proposed RCT, we will adopt Chan et al.'s version with a slight amendment of the wording to "my coach." The modified version of the HCCQ will allow us to understand parents' perceptions of the degree to which their coach is autonomy supportive (vs. controlling) in coaching them regarding their child's participation. The HCCQ has demonstrated acceptable internal consistency ($\alpha = 0.94\text{--}0.95$) in various studies.

Patient Global Impression of Change (PGIC). This measure is proposed for use, because it can provide an indicator of parents' global impression of whether their child's participation in community activities has been better, about the same, or worse since the start of the given intervention. The PGIC includes only one item that is scored on a 7-point Likert scale (1 = *very much improved* and 7 = *very much worse*). This measure has been reported to demonstrate good clinimetric properties.

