2.3 Sample Size

The sample size was calculated using Morgan and Case's formula with the following set-up: type I error of 0.05, power of 0.90, 1-to-1 random allocation, and variance ratio of 0.44, using a conservative assumption for the compound symmetry correlation structure. A large effect size (Cohen's d) of 0.80 was determined based on the pooled effect sizes derived from our previous study and a recent RCT. Therefore, a minimum sample size of 30 participants will be required in this pilot RCT to test for 2×3 mixed design analysis of covariance (i.e., the number of two groups with three repeated measurements, adjusted for individual differences in baseline assessments). Allowing for an attrition rate of 40% that was observed in the previous study, a total of 50 parent-child dyads (25 in each group) will be recruited.

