To evaluate the initial efficacy of OPC on the primary and secondary outcomes, we will use the repeated-measures analysis of covariance (ANCOVA) by controlling for baseline variability at time 0 as well as the variations in treatment dosage and delivery format (e.g., in person or tele-format). That is, the repeated-measures ANCOVAs will be used to compare the change in the scores of outcome measures across the three time points (at times 1, 2, and 3) by controlling for baseline differences and treatment variations. For participation goals identified by parents in the COPM, only community-related participation goals will be targeted for analysis. Principles of intent-to-treat analysis will be applied and, if participants withdraw after the coaching/consultation sessions, their data for subsequent time points will be imputed by carrying the last assessment forward. Post-hoc analyses using the Schffé method will be performed when the main comparison results are significant. Statistical significance will be set at $p < 0.05$. Estimates of effect sizes with 95% confidence intervals will be calculated for each outcome measure.

TABLE 1: A priori success criteria to assess the feasibility of the trial

	Definition	Success criteria
Recruitment	Percentage of eligible families agreeing to participate in the study	$\geq 20\%$ recruitment response rate achieved
Retention	Percentage of participants who complete the trial	$\geq 60\%$ retention rate achieved (i.e., completion of all assessments)
Adherence	Percentage of coaching sessions attended by parents in the intervention group	$\geq 75\%$ adherence rate achieved, based on our previous research of similar duration (42)
Blinding success	Percentage of parents who guess treatment allocation correctly after the study	50% based on the guess of treatment by chance (50/50)
Fidelity	Degree to which the OPC is implemented by coaches as intended	$\geq 80\%$ fidelity on the OPC Fidelity Measure Version 3.0 in four selected session per coach

Note: The OPC Fidelity Measure Version 3.0 consists of 18 items across five domains: relationship, goal, reflection, analysis and action, client response, and distinguishing. Each item is rated on a 3-point Likert scale (1 = *low* and 3 = *high*). The percentage score will be calculated by dividing the total score by the possible maximum score. Higher percentage scores indicate higher fidelity, and the cut-off of sufficient fidelity of OPC per session is set at 80%.

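### Section 2.8 names neither the service-hours covariate promised in 2.7.2.3.3 nor the randomization stratum, and the categories for hours have no cut-points

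*Combined protocol and SAP*

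**What the plan says.** Section 2.7.2.3.3 (Demographic questionnaire) asks parents which early intervention services the child received in the past month and for how long. It then states that the total "service hours will be categorized and used as a control variable adjusted for baseline differences in the analysis of the efficacy of OPC". Neither the number of categories nor any cut-point is given there or elsewhere.

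Section 2.8 sets out the efficacy model, a repeated-measures ANCOVA "controlling for baseline variability at time 0 as well as the variations in treatment dosage and delivery format". A second sentence restates this as adjustment for baseline differences and treatment variations. Service hours are not named in either sentence.

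Section 2.3 describes the design-stage model as "adjusted for individual differences in baseline assessments", with no other covariate. Section 2.5 stratifies the block randomization by whether the family is awaiting or receiving early intervention services. That factor does not appear in the 2.8 model either.

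**The concern.** An analyst who programs from 2.8 alone would fit a model without hours. One who also follows 2.7.2.3.3 would add them, after choosing how many groups to form and where to cut. The treatment estimate and its p-value can differ between these models. Nothing in the plan prevents the choice from being made after the outcome data are seen, in a trial that may finish with 30 participants and tests at 0.05.

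There is also a question of efficiency. Hours are collected as a quantity, and grouping them discards information if their relation to the outcome is roughly linear. Leaving them out, or leaving out the stratum that constrained the randomization, forgoes precision that the collected data could supply.

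**Working it through.** **1. The plan's own sample size.** Section 2.3 gives "type I error of 0.05, power of 0.90, 1-to-1 random allocation, and variance ratio of 0.44", and "A large effect size (Cohen's d) of 0.80 was determined". With two-sided alpha (the sidedness is not stated):

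- n per arm = 2(1.960 + 1.282)² / 0.80² = 32.84
- times the variance ratio: 32.84 × 0.44 = 14.45, rounded up to 15 per arm, so 30 in total
- with 40% attrition: 30 / 0.6 = 50

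This matches the plan. One-sided alpha would give 24. Service hours do not enter the calculation, so the point does not alter 30 or 50.

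**2. The two covariate lists.**

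| Term | 2.7.2.3.3 | 2.8 |
|---|---|---|
| Time 0 baseline | not addressed | named |
| Treatment dosage, delivery format | not addressed | named |
| Past-month service hours | named, categorized | not named |
| Awaiting/receiving stratum (from 2.5) | not addressed | not named |

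**3. What grouping or omission could cost.** Let R² be the share of the variance left after the time 0 score that hours explain. The documents give no value, so 0.05, 0.10 and 0.20 are assumptions. Let f be the fraction of R² kept after cutting a normal covariate into k equal groups: f = k × Σ(φ(a) − φ(b))², summed over groups with limits a and b. This gives f = 0.637, 0.793 and 0.861 for k = 2, 3 and 4.

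The confidence interval width relative to continuous hours is √[(1 − fR²)/(1 − R²)] for groups and √[1/(1 − R²)] for omission. For example, with a median split at R² = 0.20: √[(1 − 0.637 × 0.20)/0.80] = √1.091 = 1.044.

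| Assumed R² | 2 groups | 3 groups | 4 groups | Hours left out |
|---|---|---|---|---|
| 0 | 0 | 0 | 0 | 0 |
| 0.05 | +1.0% | +0.5% | +0.4% | +2.6% |
| 0.10 | +2.0% | +1.1% | +0.8% | +5.4% |
| 0.20 | +4.4% | +2.6% | +1.7% | +11.8% |

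**4. The same comparison as power.** This uses the noncentral t with 15 per arm, d = 0.80 and variance 0.44(1 − fR²), where f = 1 for continuous hours. Dosage and format terms are not counted. With hours left out, power is 88.9%.

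| Assumed R² | Continuous | Categorized (2-4 groups) |
|---|---|---|
| 0.05 | 90.3% | 89.8-89.9% |
| 0.10 | 91.8% | 90.7-91.2% |
| 0.20 | 94.4% | 92.5-93.6% |

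Categorized hours therefore do slightly worse than continuous hours, and better than no hours.

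**5. Why R² must be the share left after time 0.** Suppose hours explain a share m of the outcome variance overall, correlate equally with the time 0 and later scores, and those scores correlate ρ (all assumed). Then R² = m(1 − ρ) / [(1 − m)(1 + ρ)].

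- m = 0.10, ρ = 0.7: 0.111 × 0.3/1.7 = 0.02
- m = 0.20, ρ = 0.33: 0.25 × 0.67/1.33 = 0.13

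An overall share of 10-20% can thus shrink considerably once the time 0 score is in the model.

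**6. Sensitivity to a spike at zero.** Children awaiting services may report no hours. In an illustrative distribution (assumed: half zero, the rest gamma with shape 2 and scale 4), a none/any split keeps 50% of the linear signal and a none/low/high split keeps 78%. The fractions in step 3 are therefore indicative only.

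**The case against.** The strongest reply is that this is a single document whose sections should be read together. Section 2.8 does not call its list exhaustive, and its restatement refers to baseline differences, the same two words that appear in the 2.7.2.3.3 sentence on hours. On that reading, one section supplies a covariate and the other the general model. This stands as a possible reading. A reader might infer from the literal lists that the plan contradicts itself or drops hours, but the text does not establish either. Section 2.3 leans the other way, since it ties the adjustment to baseline assessments. The result is ambiguity, and the remedy is the same under both readings.

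A second reply is that little may be at stake. Section 2.6.3 expects occupational therapy within these services to have minimal influence on community participation, and 2.7.2.3.3 says only that services may matter. An R² near zero is plausible, and then nothing is lost. This also stands. A reader might infer that categorizing necessarily wastes precision, but the documents do not show that. Compared with a model without hours, categorizing gains precision if hours are prognostic. Nor does grouping always cost degrees of freedom: a two-level category uses 1, as a linear term does.

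A third reply is that hours are recalled by parents and may pile up at zero, so a straight line may fit poorly. That is fair for hours alone. It carries less weight once the awaiting/receiving stratum is in the model, because the stratum takes up most of the difference between having services and having none. Stratification also balances a main source of variation in hours, but it does not settle which model will be fitted.

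**Conclusion.** The point holds as a minor but real gap in specification. The plan promises a covariate in one section, leaves it unnamed in the section that defines the analysis, omits the stratum from that model, and leaves the form of the covariate to be chosen. The main consequence is an analysis choice left open until data are seen, rather than a demonstrated loss of precision.

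The size of any loss cannot be derived from the documents. The ranges of about 1-4% (median split) and about 3-12% (omission) rest on an assumed R² of 0.05 to 0.20 after the time 0 score, a roughly normal covariate and a linear effect. The median split is the least favourable of the equal-group cuts examined, and nothing in the plan says that it is intended. Efficacy is described as initial in a feasibility pilot, which also limits the consequence.

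**What to change.** In 2.8, give one covariate list that includes the awaiting/receiving stratum and past-month service hours from the baseline questionnaire, with hours as a continuous term. State that the therapy-activity log in 2.6.3, which records services during the study, is not the source of this covariate. In 2.7.2.3.3, keep categories for describing the groups only and refer to 2.8 for the model. If the sponsor prefers categories in the model, their number and cut-points should be fixed before any data are seen.

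The cost is about one line in each section and no new data. Hours and stratum use 2 degrees of freedom in total. At 15 per arm, if they explain nothing, this moves power from 88.9% to 88.8% in the calculation above, which does not count chance imbalance in hours. The model also then assumes approximate linearity in hours among children receiving services, which can be checked with a plot.

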2.8 Data Analysis

Descriptive statistics will be used to characterize the participants and evaluate the trial feasibility according to our a priori success criteria (see Table 1). The t-test (or Mann-Whitney U test) and chi-square statistics will be used to test for between-group baseline differences. Prior to the efficacy analyses of OPC, the normality of the data for the studied variables will be examined and, if the data are not normally distributed, transformation methods will be applied.

To evaluate the acceptability of OPC intervention, interviews with parents and coaches will be transcribed and then analyzed separately using qualitative methods. Specifically, thematic analysis using a data-driven inductive approach will be used to scrutinize the parents'

interview transcripts and interpret their coaching experience as well as perceived impact. Thematic analysis is chosen, because it provides a flexible method for identifying, analyzing, and reporting patterns (themes) within data without a prior coding scheme. Alternatively, coaches' interview transcripts will undergo conventional content analysis to describe their experience in delivering OPC intervention. We choose content analysis because only eight coaches will be involved in the proposed RCT and data saturation may not be achieved if thematic analysis is used. Two research team members will be involved in the thematic and content analyses by following the recommended procedure. To establish the trustworthiness of the thematic and content analyses, code-recode, peer checking, and team discussions will be used.

To evaluate the initial efficacy of OPC on the primary and secondary outcomes, we will use the repeated-measures analysis of covariance (ANCOVA) by controlling for baseline variability at time 0 as well as the variations in treatment dosage and delivery format (e.g., in person or tele-format). That is, the repeated-measures ANCOVAs will be used to compare the change in the scores of outcome measures across the three time points (at times 1, 2, and 3) by controlling for baseline differences and treatment variations. For participation goals identified by parents in the COPM, only community-related participation goals will be targeted for analysis. Principles of intent-to-treat analysis will be applied and, if participants withdraw after the coaching/consultation sessions, their data for subsequent time points will be imputed by carrying the last assessment forward. Post-hoc analyses using the Schffé method will be performed when the main comparison results are significant. Statistical significance will be set at $p < 0.05$. Estimates of effect sizes with 95% confidence intervals will be calculated for each outcome measure.

TABLE 1: A priori success criteria to assess the feasibility of the trial

	Definition	Success criteria
Recruitment	Percentage of eligible families agreeing to participate in the study	$\geq 20\%$ recruitment response rate achieved
Retention	Percentage of participants who complete the trial	$\geq 60\%$ retention rate achieved (i.e., completion of all assessments)
Adherence	Percentage of coaching sessions attended by parents in the intervention group	$\geq 75\%$ adherence rate achieved, based on our previous research of similar duration (42)
Blinding success	Percentage of parents who guess treatment allocation correctly after the study	50% based on the guess of treatment by chance (50/50)
Fidelity	Degree to which the OPC is implemented by coaches as intended	$\geq 80\%$ fidelity on the OPC Fidelity Measure Version 3.0 in four selected session per coach

Note: The OPC Fidelity Measure Version 3.0 consists of 18 items across five domains: relationship, goal, reflection, analysis and action, client response, and distinguishing. Each item is rated on a 3-point Likert scale (1 = *low* and 3 = *high*). The percentage score will be calculated by dividing the total score by the possible maximum score. Higher percentage scores indicate higher fidelity, and the cut-off of sufficient fidelity of OPC per session is set at 80%.

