2.5 Randomization and Blinding

Block randomization stratified by engagement in early intervention services (awaiting vs. receiving) based on the 1-to-1 allocation ratio will be used to assign participants to the intervention or control group. The randomization sequence will be computer-generated, and allocation will be completed by another research assistant not associated with the study.

Participants and independent outcome assessors will be blinded.

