2.7.2.3 Initial Efficacy of OPC

2.7.2.3.1 Primary Outcome Measures

Canadian Occupational Performance Measure (COPM). The COPM will be used to measure parents' perceptions of children's participation in specific community activities. This measure is selected for use because it can identify individualized problems in participation in occupations and then help to formulate goals related to child participation through semi-structured interviews. In the interview, parents are further prompted to rate their child's performance and their satisfaction with the current status on a 10-point Likert scale (1 = *not good/satisfied at all* and 10 = *optimal performance/satisfaction*). High scores indicate greater children's participation performance and parents' satisfaction. In this pilot RCT, we propose that parents' identified goals will not be limited to the community participation but will also be extended to other life areas. An adequate internal consistency (Cronbach's $\alpha = 0.73$ – 0.88) of the COPM has been reported. The prioritized problems using the COPM in parents of children with disabilities were also found to be corresponding with specific items in the Pediatric Evaluation of Disability Inventory, demonstrating construct validity of the COPM.

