Young Children's Participation and Environment Measure (YC-PEM). The YC-PEM will be used to capture children's overall community participation patterns. This measure is selected because it is a parent report questionnaire that can be used for young children with various disabilities. The YC-PEM also has a community section that includes 11 participation items across four broad categories of neighbourhood and community outings, classes and groups, community-sponsored activities, and recreational activities and trips. In each item, parents are asked to rate: (a) how often their child has participated in the past four months using an 8-point Likert scale (0 = *never* and 7 = *once or more each day*); (b) how involved the child is during participation using a 5-point Likert scale (1 = *not very involved* and 5 = *very involved*); and (c) parental desire for change in the child's participation (yes/no and, if yes, six nominal options for the type of desired change can be selected). Total scores are generated by averaging all items in the participation frequency and involvement dimensions. High scores indicate greater children's participation frequency and involvement. The YC-PEM participation scale has acceptable internal consistency ($\alpha = 0.64$ – 0.78) and test-retest reliability (intraclass correlation coefficients [ICC] = 0.82–0.89). Moreover, it demonstrates known-group validity between children with and without disabilities and convergent validity by correlating with functional performance of children with disabilities.

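### Section 2.8 tests raw scores for normality and transforms them if they fail, but the ANCOVA assumes normal residuals, and no original-scale result is planned

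*Combined protocol and SAP*

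**What the plan says.** Everything the plan says on distribution and scale is in one sentence of section 2.8. It begins "Prior to the efficacy analyses of OPC, the normality of the data for the studied variables will be examined" and continues "if the data are not normally distributed, transformation methods will be applied". The efficacy analysis follows in the same section: "we will use the repeated-measures analysis of covariance (ANCOVA) by controlling for baseline variability at time 0", with further adjustment for treatment dosage and delivery format, comparing the groups over times 1, 2 and 3. Section 2.8 also promises that "Estimates of effect sizes with 95% confidence intervals will be calculated for each outcome measure".

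The primary scores have defined, bounded units (section 2.7.2.3.1). For the COPM, parents "rate their child's performance and their satisfaction with the current status on a 10-point Likert scale". For the YC-PEM, "Total scores are generated by averaging all items in the participation frequency and involvement dimensions", from frequency items rated 0–7 and involvement items rated 1–5.

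The plan does not name a normality test or threshold, or a transformation. It does not say whether one scale must serve all time points and the time 0 covariate, whether results are back-transformed, or whether an untransformed analysis is also reported. Residuals are not mentioned. On blinding, section 2.5 says "Participants and independent outcome assessors will be blinded"; the analyst is not mentioned either way.

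**The concern.** The check looks at the wrong object. An ANCOVA outcome can be markedly skewed because its baseline is skewed, while the errors around the model are normal; no remedy is then needed. Conversely, a normal baseline can mask skewed errors, so that the raw score passes and the real departure goes unseen. A rule based on the raw score can therefore fire without need and stay silent when there is something to see.

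Firing has a cost. The main comparison is of change between groups over time, and equal changes on an instrument are not equal after a nonlinear change of scale. Because the transformation is left open and depends on the trial's own data, the question asked of a primary outcome would be settled after the data are seen. The reported effects could be in log or root units for some scores and instrument units for others.

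**Working it through.** **Inputs from the plan (section 2.3).** The sample size rests on "type I error of 0.05, power of 0.90, 1-to-1 random allocation, and variance ratio of 0.44", with d = 0.80, a minimum of 30 participants, 40% attrition and 50 recruited (25 per arm). Sidedness is not stated.

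**Reproducing the plan's figure.** n per arm = 2 × (z₀.₉₇₅ + z₀.₉₀)² × variance ratio / d² = 2 × (1.960 + 1.282)² × 0.44 / 0.80² = 21.01 × 0.6875 = 14.4, rounded up to 15, so 30 in total (approximate power 0.91). A one-sided calculation gives 24 and does not match, so two-sided testing is assumed. Allowing for attrition, 30 / (1 − 0.40) = 50. Both figures reproduce, and neither depends on the transformation rule.

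**Simulation set-up.** Outcome = d × group + 0.75 × baseline + √(1 − 0.75²) × error. The 0.75 is chosen because 1 − 0.75² = 0.4375 ≈ 0.44, the plan's variance ratio. The model is a baseline-adjusted ANCOVA with one post-intervention score, 8,000 runs per setting. Three things are assumptions because the plan names none of them: Shapiro-Wilk at 0.05, exponential skew, and log or square root as the transformation.

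**How often each check flags, no treatment effect.**

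| Setting | Per arm | Raw-score check | Residual check |
|---|---|---|---|
| Skewed baseline, normal errors (assumption holds) | 15 | 28% | 5% |
| Same | 25 | 43% | 5% |
| Normal baseline, skewed errors (assumption fails) | 15 | 18% | 85% |
| Same | 25 | 26% | 99% |

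With d = 0.80, the raw-score figures are 21% and 31% where the assumption holds, and 13% and 20% where it fails; the residual figures are essentially the same as in the table. A second simulation at 25 per arm with the same assumed test and skew gave 42% against 5%, and 28% against 99%.

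**Effect on error rates.**
- Type I error, untransformed ANCOVA: 4.3–5.0% (up to 5.6% in the second simulation).
- Type I error, log transform whenever the raw score is flagged: 4.5–5.0% (4.4–5.5% in the second).
- Type I error, smallest p of raw, log and square root once flagged: 4.7–5.6% (at most 5.9% in the second).
- Power at d = 0.80, 15 per arm: 0.87–0.88 both untransformed and under the log rule.

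The Monte Carlo standard error near 5% is √(0.05 × 0.95 / 8000) ≈ 0.24 percentage points.

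**What a change of scale does to the contrast (invented values).** Suppose mean COPM scores go from 3 to 6 in one group and from 4.5 to 7.5 in the other. On the instrument both change by 3 points, so there is no group-by-time difference. On the log scale the changes are ln(6/3) = 0.69 and ln(7.5/4.5) = 0.51, so there is one.

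**The case against.** The strongest reply is that this is an ordinary gap in specification, in a pilot whose efficacy aim is called initial, and that it does little measurable harm. Much of that stands, and it rules out several stronger readings.

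- A reader might infer that choosing the scale after seeing the data inflates the false-positive rate. The documents do not support this for the rule as written: it is triggered by normality, not by p-values, and nothing in section 2.8 lets the analyst keep the smallest p. The simulated error rates stay close to 5%. Larger inflation needs undisclosed picking across several scales, which is not the plan.
- A reader might count the scores and visits and predict how many false flags will occur. The plan says only that normality will be examined, which could mean plots or skewness. The flag rates above illustrate the mismatch; they do not forecast this trial, for which the documents give no score distributions.
- A reader might say that transformed effects could not be set beside d = 0.80. That is too strong, since a standardised effect has no units. In an assumed COPM-like case the residual-standardised effect was 0.86 raw, 0.85 root and 0.81 log, though 0.68 inverse. It would still be standardised on a different scale, and the shift depends on a transformation nobody has named.
- A reader might treat these effect sizes as the pilot's main product for a definitive trial. The introduction puts feasibility and acceptability first, Table 1 sets success criteria only for feasibility, and nothing says that the estimates will size a later trial.

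One defence does not work: that the normality sentence could loosely mean residuals. It refers to the studied variables and places the check before the efficacy analyses, when no residuals yet exist.

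**Conclusion.** The point holds as a matter of interpretability and pre-specification, and the sponsor should act on it; it does not threaten the validity of the test. The plan states a rule, and the rule checks the wrong quantity. At 25 per arm it would transform in about 42% of trials that need nothing and would miss roughly three in four of those where residuals are clearly non-normal (flagging 26–28%, against 99% for a residual check). Type I error stays at or below about 6% and power is almost unchanged. The original-scale ANCOVA held its error rate in every setting tried, so there is little for a transformation to repair.

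These sizes rest on Shapiro-Wilk at 0.05, exponential skew, a baseline correlation of 0.75 and a single post-intervention score in place of the three-visit model. That the check falls on raw variables, that the scale is left to depend on the data, and that no original-scale result is promised all come directly from section 2.8 and need no assumption. The loss of instrument units affects only those outcomes for which the rule fires. As the analyst's blinding is not described, the documents do not show that the scale would be chosen with knowledge of allocation.

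**What to change.** Replace the normality sentence in section 2.8 with three commitments:

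1. The ANCOVA on the original instrument scale is the primary analysis for every primary and secondary score, whatever its distribution, and effects and intervals are reported in those units.
2. Assumptions are judged on the residuals of the fitted model. The findings are described but do not change the primary analysis.
3. One sensitivity method, named in advance, is reported for all outcomes and is not triggered by the data; for example, a participant-level bootstrap confidence interval from the same model. Any transformation is named beforehand and used only as a sensitivity analysis.

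A re-randomisation test is a less convenient choice for item 3: allocation is blocked within strata, and the model adjusts for dosage and delivery format, which can depend on the arm.

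The cost is a few sentences in the plan and a little more analysis work. There may be a slight loss of power for very skewed secondary scores; with skewed errors the simulations show about one percentage point (0.868 against 0.880 at 15 per arm, 0.973 against 0.981 at 25). The sample size of 30, and 50 recruited, does not change.
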